12.2 Secondary Objectives

1. To compare the duration of protection offered by different repellent products using the median Complete Protection Time (mCPT)
2. To compare the effectiveness of protection offered by different repellent products using the median effective dose and median effective time
3. To assess the acceptability of the repellent products tested in the field trials using qualitative data from participants.

13 Trial Design

This is a within-subject, non-masked, trial of the use of commercially available insect repellents against *Musca sorbens*, with two consecutive participant groups in the laboratory and in the field, and a primary endpoint of measuring the protective efficacy of each repellent product.

The trial is within-subject to allow comparison of *M. sorbens* contacts on the same participants both before (control) and after (test) application of the repellent or repellent device. This is to mitigate any possible inter-individual attractiveness effects. Control sampling will be conducted before test sampling, to preclude contamination of the control sampling by the test sampling. For this reason, the trial is not masked.

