13.1 Laboratory trial

In preliminary laboratory clinical trials in London, 17 participants will test all products that have been found to exhibit repellency to *Musca sorbens* in benchmarking laboratory studies. These will be chosen from: DEET (N,N-diethyl-3-methylbenzamide), IR3535 (3-[N-butyl-N-acetyl]-aminopropionic acid ethyl ester), Picaridin (2-(2-hydroxyethyl)-1-piperidinecarboxylic acid 1-methylpropyl ester); PMD (para-Menthane-3,8-diol) or permethrin (m-Phenoxybenzyl)-cis,trans-3-(2,2-dichlorovinyl)-2,2-dimethylcyclopropanecarboxylate). Products tested will be either (1) topical repellents, or (2) in long-lasting, plastic formulations of repellents that can be worn on the body (wearable repellent technologies). The insect repellent synergist Vanillin (4-Hydroxy-3-methoxybenzaldehyde) may be added to the long-lasting plastic formulations, to improve the duration of protection.

As all participants will test all products and all concentrations, this study is non-randomised. The combination of product and product format to be tested will be determined before the study commences. Participants will be asked to place their arm in a cage with 100 *Musca sorbens* flies, and the behaviour of the flies on the surface of the arm and hand will be filmed for ten minutes. This modified arm-in-cage assay has been developed specifically for use with *Musca sorbens*.

There will be a two-stage selection process to determine which repellent products, at which concentration (dose), should be carried forward to the field trial. In the first stage, a single measure of Protective Efficacy (PE) will be used to determine protection, by measuring the duration of fly-arm contact after application of a repellent product (test measurement) relative to that before application of the product (control measurement). By only selecting repellent products/concentrations that protect against at least 30 % of fly contact immediately following application (at time zero), those with little or no effect will be disregarded.

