17.2 Secondary outcome measures

1. Median Complete Protection Time (mCPT) in laboratory trials only
2. Median Effective Dose (ED₅₀), in laboratory trials only
3. Median Effective Time (ET₅₀), in both laboratory and field trials
4. Acceptability of the repellent interventions among children and their caregivers, in field trials only

18 Participant timeline

A timeline of participant recruitment and enrolment, consent, and completion of the clinical trials is given in Figure 4.

Figure 4. Participant timeline for clinical trials of insect repellents against fly contact by *Musca sorbens*

19 Sample size

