19.2 Field trials sample size

This trial will be powered to detect a protective effect in the intervention (treatment) groups relative to the control groups. To test for 30 % protection (PE) in the intervention arm versus the control arm, assuming a standard deviation of 30% and using 90 % power, 23 children are required in each study group. When allowing for 25 % loss-to-follow-up, the total sample size in each study arm will be 29 people. Equal numbers of male and female participants are preferred.

Not all approximately participants in the wearable repellent device arms of the field trial will be interviewed for intervention acceptability. Based on previous experience, we anticipate that a sample of 15 to 20 child-caregiver pairs, purposively sampled to represent the range of child ages will be sufficient, and further data collection unlikely to yield additional information. However, we will review our data regularly during the data collection process and will adjust the sample accordingly.

20 Enrolment, randomisation and allocation

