21.1.3.2 Persistence

Having established which repellent products are effective at which doses, the persistence of all repellent products at doses achieving at least 30 % protection (at time zero) will be determined. Persistence will be determined using an extended version of the protocol described in 21.1.3.1. Preparation, and control testing, will be conducted in the same manner, then the repellent products at the appropriate dose will be applied and tested for ten minutes as previously, and the observation will be repeated every hour for six hours (Figure 5). After testing, the participant will be given access to washing facilities to wash off the topical repellent. This data will allow calculation of the Median Protection Time/Effective Dose (ET_{50} and ED_{50}). To determine the Median Complete Protection time (mCPT), the same protocol will be used however the first test sampling period will be extended until the first fly-arm contact.

[figure not shown]

Figure 5. Timescale for repellency complete protection time (CPT), and median protection time, testing in the laboratory.

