22.5 Benefits associated with participation

Participants in the laboratory trial will receive no benefits from participation in the trial. Participants in the field trial will have the opportunity to have their vision and eyes checked by the Stronger-SAFE project team, and will receive appropriate referral for identified problems. There are no further benefits expected for any participants.

23 Modifications

Should it be necessary in the field trials, lower dose topical repellents can be substituted to improve tolerance to the facial application (e.g. in the event of discomfort), provided those lower doses were found to provide at least 30 % protective efficacy.

24 Adherence

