26.3.3 Median Effective Dose (ED₅₀) and Median Effective Time (ET₅₀)

ED₅₀ and ET₅₀ will be calculated in stage two ('persistence') laboratory trials, however, as only one dosage level will be used in the field only ET₅₀ will be estimated there.

The relationship between Protective Efficacy and repellent dose and time since treatment can be estimated using a probit-plane regression model (Equation 2). The coefficient b_1 provides an estimate of the effect of repellent dose on p , and b_2 provides the effect of the time since treatment on p .

Once these coefficients have been estimated, then we can estimate the ED₅₀, concentration (dose) of repellent product that affords 50 % protection from fly contacts at time zero (the time of application). This is done by setting $p=0.5$ and $t_1=0$ and then solving equation 2. We can also estimate ET₅₀, estimating the persistence of the protective effect of a repellent product for a given dosage, using the same method.

Equation 2. Probit-plane regression model for ED₅₀ and ET₅₀

$$\ln [p / (1 - p)] = a + b_1(D_0) + b_2 t_1$$

Where:

- p is as above, estimated from
 - Total duration of fly-arm contact (laboratory trials)
 - Total frequency of fly-eye contacts (field trials)
- D_0 is the dose calculated as the natural logarithm of the dose applied ($\ln[\text{dose}]$)
- t is the time post-treatment in hours
- a , b_1 and b_2 are coefficients estimated using the probit-plane regression model

In the laboratory trials, p will be estimated by the total duration of fly-arm contact, while in the field trials p will be estimated using the total frequency of fly-eye contacts, as defined in section 26.3.1.

27 Monitoring

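### ET50 is negative, so not a duration, for any decaying product that starts below 50% protective efficacy; the plan keeps products from 30% and has no rule for this case

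*Combined protocol and SAP*

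**What the plan says.** Equation 2 (26.3.3) models the log odds of PE as linear in log dose and in hours since treatment. ED50 is the dose at which p = 0.5 at time zero. ET50 is introduced as "estimating the persistence of the protective effect of a repellent product for a given dosage, using the same method", which puts it at p = 0.5 as well.

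ET50 has a stated job. Secondary objective 2 (12.2) reads "To compare the effectiveness of protection offered by different repellent products using the median effective dose and median effective time". Section 17.2 lists "Median Complete Protection Time (mCPT) in laboratory trials only", confines ED50 to the laboratory too, and gives ET50 for both settings. ET50 is therefore the only listed measure of duration in the field, and 13.2 says the repeated field sessions are there to obtain it.

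The working threshold is 30%, not 50%. Section 21.1.3.2 says "the persistence of all repellent products at doses achieving at least 30 % protection (at time zero) will be determined". Section 21.1.3.1 defends a threshold below the customary 50%. Section 19.2 sizes the field trial at 30% PE. Section 23 allows lower field doses, "provided those lower doses were found to provide at least 30 % protective efficacy". Section 16.2.2 warns that efficacy may be lower in the field than in the laboratory.

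**The concern.** A product that never reaches 50% has no time at which it falls to 50%. Equation 2 still returns a number: the time before application at which the fitted line would have crossed 50%. That number says the product started below 50%, but nothing usable about how long its protection lasts. Compared between products, it favours the faster decay.

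The plan deliberately admits products between 30% and 50%. At its own field design value it could show protection and have no listed outcome that describes the duration. A replacement would then be chosen after the data had been seen. In the laboratory, ET50 is one input to the choice of products for the field, so the effect there is partial.

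**Working it through.** **Design point.** A two-sample t calculation with difference 30 points, SD 30 points, 90% power and two-sided 5% alpha (alpha is not stated, so this is an assumption) gives 22.02, hence the 23 per group in 19.2. The trial is thus built around a product that starts at 30%.

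**Formula.** Setting p = 0.5 makes the left side of Equation 2 zero, so ET50 = −(a + b1·ln dose)/b2 = −logit(p0)/b2. With b2 < 0 and p0 < 0.5, ET50 < 0. Its derivative with respect to b2 is logit(p0)/b2², which is negative, so a steeper decline gives a larger (less negative) ET50. Neither result depends on an assumed figure. If the fitted b2 were positive, ET50 would be positive for p0 < 0.5, which is not a duration of protection either.

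**Illustration.** The documents give no decay rates, so the slopes are assumptions. PE(t) = invlogit(logit(p0) + b2·t).

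| Start p0 | b2 per hour | ET50 (h) | PE at 6 h |
|---|---|---|---|
| 30% | −0.1 / −0.3 / −0.5 | −8.47 / −2.82 / −1.69 | 19.0 / 6.6 / 2.1% |
| 40% | −0.1 / −0.3 / −0.5 | −4.05 / −1.35 / −0.81 | 26.8 / 9.9 / 3.2% |
| 60% | −0.1 / −0.3 / −0.5 | +4.05 / +1.35 / +0.81 | 45.2 / 19.9 / 6.9% |

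Example: logit(0.40) = −0.405, and −(−0.405)/(−0.1) = −4.05 h. Above 50% the order is right; below 50% it is reversed. A probit link gives the same signs (30% start: −5.24 h at slope −0.1, −1.05 h at −0.5).

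**How often p0 would be below 50%.** With n = 23 and SD 30%, the chance that the observed time-zero mean is below 50% is Φ((0.50 − m)/(0.30/√23)): 99.9%, 94.5% and 79% at true PE m of 30%, 40% and 45%.

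**Simulation.** Two products share a start and have slopes −0.1 and −0.3; SD 30%; within-person correlation 0 or 0.5; n = 23 over hours 0–5 (field) or n = 17 over hours 0–6 (laboratory); one dose per product; Equation 2 fitted to the mean PE at each time, leaving out means at or below zero. Share of runs that favour the slower-decaying product, at 30% and 40% starts:

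- raw ET50: about 14–32%
- fitted PE at the last hour: about 93–100%
- b2: about 87–99%

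At a 70% start, ET50 is right in about 94–99%. At SD 15% and a start of 30% or 40%, it is right in only about 0.5–7%. Less noise makes it worse, so the reversal is structural.

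**Limit of any fitted value.** At a 30% start with slope −0.5 and n = 17, about 15% of pooled points (39% at 6 h) are at or below zero and have no logit. Leaving them out flattens the fitted slope from −0.50 to between about −0.36 and −0.40.

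**The case against.** Several points on the other side stand.

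- A reader might infer that the reversal could mislead the choice of dose. It cannot. In Equation 2 the doses of one product share one b2, so with decay the dose with the higher start always has the larger ET50. The reversal arises only between products that are both below 50%. A product above 50% still ranks above them.
- A reader might infer that the plan will rank negative times. No passage says so, and a statistician would recognise a negative value. The simulated shares describe a comparison the plan does not spell out; they measure how poorly raw ET50 serves objective 2.
- A reader might infer that persistence is left with nothing. PE at each time must be computed as input to Equation 2, 26.3.3 interprets b2 as the effect of time, and b2 orders decay correctly. But b2 is neither a duration nor a listed outcome, and no table of PE by time is specified.
- A reader might infer that only three estimates inform selection for the field. The list in 13.1 is introduced as inclusive, so it is not closed.
- 30% is an entry floor and a design effect, not a forecast. The documents give no PE for any product, and all may exceed 50%.

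These points narrow the matter. They do not supply the missing rule.

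**Conclusion.** The point holds as a gap in the definition of a secondary outcome and should be fixed. For a decaying product with fitted time-zero PE below 50%, ET50 is negative and is not a duration; between two such products with the same start, it favours the faster decay. This follows from Equation 2 alone. The sizes shown rest on assumed slopes and on the plan's SD of 30%.

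The primary outcome, mCPT, ED50, products above 50% and the ordering of doses within a product are not affected. The documents do not support a claim that selection for the field will go wrong, because ET50 is one input among several and no passage commits to ranking negative values. In the field the gap matters more, since no other duration outcome is listed.

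**What to change.** Change the wording of 26.3.3 only:

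1. Keep Equation 2 and ET50. Report *below 50% at time zero* in place of a negative ET50, and do not compare products on it.
2. Make observed PE at each planned time point the main persistence summary in laboratory and field, pooled as 1 − (total T/total C). Take intervals from resampling participants, so that one person's sessions stay together. Show b2 and fitted PE beside it.
3. In the field, show the same after/before ratio for the untreated group at each hour and express each product's PE relative to it: 1 − (product ratio/untreated ratio). Section 13.2 includes that group for comparison across the day, and 21.2.1 notes that fly activity varies by time of day; otherwise that change would read as decay. For wearables at follow-up visits, use the control measured at that visit (21.1.4, 21.2.4).
4. Optionally add ET30, the time until fitted PE falls to the plan's own 30%. Report *below threshold at time zero* when it is negative, and note that it is uninformative for a start near 30% (it is 0 at exactly 30%, whatever the decay).
5. Show time points with pooled p at or below zero in the table. State that leaving them out of the fit flattens the slope, so fitted values are supportive only.

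The cost is wording: no new data, visits or participants. The downside is precision. At n = 23 and SD 30%, the 95% half-width is about 8–12 points for fitted PE and 1.96 × 30/√23 = 12.3 points for observed PE at one time. If the untreated group has the same size and SD and a ratio near 1, adjustment widens the latter to about 15 points at 30% PE (12.3 × √(1 + 0.7²)) and 17 points at zero PE (12.3 × √2).

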In the second stage and using the same participants, those repellent products/concentrations that demonstrated at least 30 % PE will be measured for the persistence of effect, over a six-hour period. For the wearable repellent devices, tests will further be repeated at one, two, three and four weeks later. The duration of fly contact in a modified arm-in-cage assay will again be used. This stage will allow estimations of persistence including the Median Effective Dose (ED_{50}), the Median Effective Time (ET_{50}) and the Complete Protection Time. Estimations of persistence will allow final selection of repellent products/concentrations to be tested in the field trials.

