16.2.1 Laboratory trials application rate

The arm is an estimated 9 % of the adult body surface area (BSA), therefore the forearm and hand can be considered to be 4.5 %. With the average adult BSA of 19,000 cm², the surface area of the forearm can be taken to be 855 cm². As such, 1.4 ml of solution will be applied to the forearm at the appropriate concentration, never exceeding 20 %.

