21.2.3 Topical repellents

Eligible **participants** will be randomly allocated in equal proportions to the study groups, as per section 13. The repellent products and product formulations to be tested will be determined before the study commences. Each study participant will test only one product type, to minimise participant discomfort. Participants will be advised not to apply any cosmetics associated with a strong scent, such as perfume, hand cream, body wash, or other scented products. Additionally, volunteers will be asked not to consume spicy foods, i.e. curries, chillies and garlic for the 12 hours prior to the tests. This will be verified with the participants prior to the commencement of any tests.

The participants face will first be washed with unscented soap then rinsed with water and towel dried. The participant will then be seated comfortably on a chair outside their house, facing the investigators (entomological field worker and nurse), and will be instructed to refrain from touching the face or brushing away landing flies. For the first test, the diluent alone (50 µL) will be tested as a control. This will be applied to the participant's face (cheeks) and allowed to dry for one minute. The participant's face will then be videoed for ten minutes by the investigator or field laboratory assistant. During this time period, fly behaviour will be manually recorded and scored. The video footage will retrospectively be analysed for (i) fly-eye (ii) fly-nose (iii) fly-mouth and (iv) fly-face contact. After this ten-minute period of control measurements, the pre-allocated topical repellent will be applied to a circular area on the participant's cheek by the Stronger-SAFE field

team nurses. Topical repellents will be applied in a 6 cm diameter circle on the cheek, at least 3 cm below the eye and positioned away from the nose and mouth. The repellent will be allowed to dry for one minute, then the videoing and observation will be repeated for another ten-minute period. Test measurements will then be repeated hourly for five further time points (Figure 7). After the final time point, the participant will be provided with soap and water to clean off the topical repellent.

[figure not shown]

Figure 7. Study design for estimation of personal protection by topical repellents from fly-eye and fly-face contacts by *Musca sorbens*. This process will be repeated for each of 29 participants.

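### Section 26.3.3 solves Equation 2 for ET50 and ED50 with no limit to the tested times or doses, so some products would get extrapolated or impossible values

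*Combined protocol and SAP*

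**What the plan says.** Equation 2 is a straight line on the logit scale in ln(dose) and time. For ED50 the instruction is: "This is done by setting $p=0.5$ and $t_1=0$ and then solving equation 2". ET50 follows for a fixed dose, "estimating the persistence of the protective effect of a repellent product for a given dosage, using the same method". Both are calculated in stage two of the laboratory trials. For the field, "as only one dosage level will be used in the field only" ET50 is estimated there. No section states what to do when the solution falls outside the tested times or doses, and no confidence interval is specified for either quantity.

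The tested range is fixed elsewhere:

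- **Laboratory topicals (21.1.3.2):** "the observation will be repeated every hour for six hours".
- **Field topicals (21.2.3):** a reading after application, then "Test measurements will then be repeated hourly for five further time points". That puts the last reading at about five hours, whereas section 13.2 describes six. The two sections need to be reconciled.
- **Dose (16.2.1):** "1.4 ml of solution will be applied to the forearm at the appropriate concentration, never exceeding 20" per cent. Section 21.1.3.1 gives five increasing doses with the same maximum.
- **Entry to stage two (21.1.3.2):** doses with at least 30% PE at time zero.

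The estimates have two uses. Secondary objective 2 (section 12.2) is "To compare the effectiveness of protection offered by different repellent products using the median effective dose and median effective time". Section 13.1 adds: "Estimations of persistence will allow final selection of repellent products/concentrations to be tested in the field trials".

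**The concern.** ET50 and ED50 are defined by a 50% crossing, but the design does not ensure that a crossing is observed. A good topical may still be above 50% when readings stop. A product admitted on the 30% criterion may never reach 50% at any dose. Solving Equation 2 returns a number in both cases, and nothing in the plan marks it as different from an estimate supported by data.

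For a durable product, the number depends on a shallow slope and on the straight line holding beyond the last reading. If noise makes the fitted slope flat or upward, the solution is infinite or negative for a product that protected throughout. What the trial can support for such a product is that ET50 exceeds the last reading time. The products with the least supported ET50 are therefore likely to be the most durable ones, which the comparison is meant to find.

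**Working it through.** The plan states no expected ET50 or ED50, so there is no figure to reproduce. All PE profiles below are assumptions.

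**ET50 for a product that outlasts the readings.** Assume PE 90% at 0 h and 80% at 6 h.

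- logit(0.9) = 2.197 and logit(0.8) = 1.386.
- Slope b2 = (1.386 − 2.197)/6 = −0.1352 per hour.
- ET50 = 2.197/0.1352 = 16.3 h, about 2.7 times the six-hour observation period.

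Other curves through the same two points:

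| Curve | Calculation | ET50 |
|---|---|---|
| Logit linear in t² | √(2.197 × 36/0.811) | 9.9 h |
| PE linear in t | 0.4/(0.1/6) | 24.0 h |
| PE exponential in t | 6 × ln(0.9/0.5)/ln(0.9/0.8) | 29.9 h |

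Other assumed laboratory profiles under Equation 2: 90% to 70% gives 9.8 h, 80% to 70% gives 15.4 h, and 70% to 65% gives 22.3 h. Inside the range the method behaves well: 70% to 30% gives 3.0 h.

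**Sampling error, one dose.** Inputs: 16 evaluable laboratory participants and PE SD 30% (section 19.1), readings at 0-6 h; 23 evaluable field participants and the same SD (section 19.2), readings at 0-5 h. The true line is the one above. Each mean PE has normal error SD/√n and is clipped to 1-99%; a least-squares line is fitted on the logit scale and ET50 = −a/b. The within-person correlation is assumed to be 0.5 or 0.

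| Setting, SD 30% | Slope zero or upward, correlation 0.5 | Correlation 0 |
|---|---|---|
| Laboratory, one qualifying dose | about 5% of trials | about 13% |
| Field | about 7% | about 15% |

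In the laboratory setting, the central 95% of ET50 estimates runs from about 10.3 to 36 h at SD 15% and correlation 0.5. At SD 30% and correlation 0 it runs from about 7.5 h with no upper limit. By contrast, a true ET50 of 3.0 h, inside the readings, is estimated at 2.1-3.9 h even with independent errors at SD 30%.

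**Sampling error, several laboratory doses.** Equation 2 shares one b2 across doses. With three doses pooled (assumed starting PE 60%, 80% and 90%), the slope is zero or upward in 0.6% of trials at correlation 0 and 0.05% at 0.5.

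**ED50 when the top dose is below 50% PE.** Assume two doses that both qualify for stage two: PE 40% at the 20% dose, and 30% or 32% at the 10% dose.

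- b1 = [logit(0.40) − logit(PE at 10%)]/ln 2 = (−0.405 + 0.847)/0.693 = 0.637, or (−0.405 + 0.754)/0.693 = 0.503.
- ED50 = 20 × exp(0.405/b1) = 38% or 45%.

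The solution can also be physically impossible: PE 30% at the 20% dose with an assumed b1 of 0.5 gives 20 × exp(0.847/0.5) = 109%. With a single qualifying dose, the design matrix has rank 2 for three coefficients, so b1 and ED50 cannot be estimated.

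**ET50 when PE starts below 50%.** A fall from 40% to 20% over six hours gives −2.5 h. Stage two admits such products.

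**The case against.** The strongest reply is that the problem is narrower than it first appears. Several stronger readings that a reader might infer are not supported.

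- **That every product below 50% PE at the 20% cap gets an untested ED50.** It does not. Below 30% PE at every dose there is no stage two, and with one qualifying dose there is no ED50. The problem is confined to the 30-50% band with at least two qualifying doses and a rising dose response. Section 21.1.3.1 also sums serial doses. If D0 uses that scale, the limit is the highest dose on it, not 20%.
- **That laboratory slopes would often be unusable.** The 5-13% figure applies to a single-dose fit; pooling b2 over three doses brings it below 1%.
- **That the simulated noise is typical.** It is severe. For PE confined to 0-100% with mean 90%, 30 points is the largest possible SD (100 × √(0.9 × 0.1)), although negative PE would allow more. All readings on a person share one control value, so zero correlation is unlikely and the lower end of each range is more credible.
- **That product selection would rest on slope noise.** Section 13.1 also uses Complete Protection Time, and section 26.3.2 estimates its median by Kaplan-Meier, which can handle replicates with no landing by the end of testing.

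All four limits stand. They do not remove the gap: the solving rule has no range condition, and pooling steadies b2 without making the line valid beyond six hours. Nor does Kaplan-Meier for one outcome tell the analyst how to report another.

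**Conclusion.** The point holds in a limited form. As written, section 26.3.3 returns an extrapolated ET50, or no forward ET50, for a topical with fitted PE above 50% at the last reading. It returns an ED50 above the tested range for a product in the 30-50% band with two or more qualifying doses and a rising dose response. In the assumed 90% to 80% profile the choice of curve alone moves ET50 between 9.9 and 29.9 h. A non-negative slope occurs in about 5-15% of single-dose fits at SD 30%, and in under 1% of laboratory fits pooled over three doses.

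How often this arises depends on PE profiles that the documents do not give. Secondary objective 2 is affected, and so in part is field selection; the primary endpoint is not. The change should be made before data are seen, because these estimates help decide which products go forward.

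**What to change.** Add to section 26.3.3:

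> ET50 and ED50 are reported as point estimates, with 95% CI, only when they lie inside the tested range. If fitted PE at the last scheduled reading exceeds 50%, ET50 is reported as greater than the last reading time, whatever the sign of the slope. If fitted PE is below 50% at time zero and at the last reading, ET50 is reported as not reached (50% protection not attained). If fitted PE at time zero is below 50% at the highest tested dose, on the same dose scale as D0, ED50 is reported as greater than that dose; if it is above 50% at the lowest tested dose, as less than that dose. With a single qualifying dose or a non-positive dose slope, ED50 is reported as not estimable. Products that outlast the readings are compared on fitted PE with 95% CI at the last scheduled reading.

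Apply the same rule to wearables, with the week-four reading as the limit. State which dose scale defines D0, and reconcile the last field reading between sections 13.2 and 21.2.3.

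The ET50 bound should depend on fitted PE, not on slope alone. A rule that reported every non-negative slope as outlasting the readings would give that label to a product flat at 40% PE in about half of trials.

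The cost is a short paragraph and no new data. The downside is that the most durable products get a bound, such as more than six hours, instead of a single ET50.
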